## RESULT

A total of 66 elderly participants in the study, divided into the "SI Kumbang" and "Bugar Lansia" gymnastic exercise group. Table 1 summarizes the baseline characteristics of the subjects. Both groups have similar characteristics.

Table 1. Baseline Characteristics

| Characteristics               | Si Kumbang
(n=33) | Bugar Lansia
(n=33) |
|-------------------------------|----------------------|------------------------|
| Age (years), mean (SD)        | 65,25 (3,25)         | 65,14 (2,99)           |
| Body Mass Index, mean (SD)    | 23,5 (22,7)          | 22,95 (21,6 – 24,2)    |
| Normal                        | 31 (86,1)            | 31 (86,1)              |
| Overweight                    | 5 (13,9)             | 5 (13,9)               |
| Gender, n (%)                 |                      |                        |
| Female                        | 36 (100,0)           | 36 (100,0)             |
| Living History, n (%)         |                      |                        |
| Alone                         | 8 (22,2)             | 5 (13,9)               |
| Husband                       | 25 (69,4)            | 30 (83,3)              |
| Childs                        | 2 (5,6)              | 1 (2,8)                |
| Siblings                      | 1 (2,8)              | 0 (0)                  |
| Educational Background, n (%) |                      |                        |
| No Education                  | 1 (2,8)              | 2 (5,6)                |
| Primary                       | 2 (5,6)              | 5 (13,9)               |
| Secondary                     | 5 (13,9)             | 3 (8,3)                |
| High School                   | 16 (44,4)            | 14 (41,7)              |
| University                    | 12 (33,3)            | 11 (30,6)              |
| Comorbid                      |                      |                        |
| Diabetes Mellitus             | 8 (22,2)             | 3 (8,3)                |
| Hypertension                  | 10 (37,8)            | 11 (30,6)              |
| Use of Diabetes Mellitus      | 8 (23,2)             | 3 (5,6)                |
| Medication                    |                      |                        |
| Use of Hypertension           | 10 (37,8)            | 11 (30,6)              |
| Medication                    |                      |                        |

SD (standard deviation)

Baseline characteristics of clinical outcomes of physical performance and immunity in elderly prior to intervention. Both groups are similar except for IL-18, which will be adjusted using ANCOVA analysis.

Table 2. Baseline Characteristics of Physical Performance and Immunity in Elderly before Intervention

| Variabel   | Si Kumbang
(n=33) | Bugar Lansia
(n=33) |
|---|------------------------------|--------------------------------|
| The Six-Minute Walk Test (6MWT) (meters), median (IR)              | 344,75 (293,75 – 376,5)      | 353 (311,25 – 375,75)          |
| Handgrip strength (kg), mean (SD)                                  | 16,11 (3,30)                 | 16 (3,39)                      |
| Skor The Short Physical Performance Battery (SPPB), median (RIK)   | 9 (9 – 11)                   | 9 (8,25 – 10,75)               |
| Skor The Physical Activity Scale for the Elderly (PASE), mean (SD) | 19,31 (2,73)                 | 20,67 (3,97)                   |
| CASPASE-1, mean (SD)   | 52251,52 (26750,02)          | 56129 (25767,23)               |
| IL-18, median (IR)   | 186,77 (136,37 – 295,03)     | 279,56 (190,67 – 438,45)       |

IR (interquartile range); SD (standard deviation)

The impact of the SI Kumbang group and Bugar Lansia group gymnastic exercise interventions on physical performance and immunity are displayed in Table 3. SI Kumbang group had significantly impact in cardiorespiration endurance (6MWD) ( $p=0.005$ ) and physical activity (PASE) ( $p = 0.001$ ). However, there was no significant impact on strength muscle (handgrip JAMAR) ( $p=0,136$ ), and balance (SPBB) ( $p=0,194$ ). Immunity in elderly showed, both group there were no significant in inflamasome Caspase-1 ( $p=0,055$ ) and IL-18 ( $p=0,327$ ). For IL-18, adjustment was performed using the ANCOVA test ( $p=0.255$ ).

Table 3. Impact Of “SI Kumbang” Exercise and “Bugar Lansia” on Physical Performance and In Elderly Analysis

| Variables                            | “SI Kumbang”
group (n=33) | “Bugar Lansia”
group (n=33) | p           | Adjusted |
|---|--------------------------------------|--|--------------------|-----------------|
|   | $\Delta$                             | $\Delta$                               |                    |                 |
| The Six-Minute Walk Distance (6MWD) (meter) | 81 (57,25 – 119,5) d      | 54 (25 – 76,5) d            | 0,005 d |                 |

|  |                                      |                                      |                                       |
|--|--------------------------------------|--------------------------------------|---------------------------------------|
| Handgrip strength (kg)                             | 1,14 (2,69) c             | 2,06 (2,27) c             | 0,136 c                    |
| The Short Physical Performance Battery (SPPB)      | 3 (1 - 3) b               | 2 (0 - 3) b               | 0,194 d                    |
| The Physical Activity Scale for the Elderly (PASE) | 5,39 (4,38) c             | 1,16 (5,26) c             | 0,001 c                    |
| Caspase-1  | -38945,33
(27628,63) c | -24957,94
(30423,15) c | 0,055 c                    |
| IL-18  | -0,03 (-44,28 – 30,84)               | 10,41 (-26,9 – 47,32)                | 0,327 d 0,255 e |

a Normally distributed variables presented as mean  $\pm$  Std. Deviation; b Non-normally distributed variables presented as Median (range); c Independent t test; d Mann-Whitney U test; e Adjusted with ANCOVA analysis

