### Abstract

**Background:** The most common issue associated with aging is frailty, which has a significant impact on the physical performance and immunity of older adults. Exercise is the primary modality in medical rehabilitation. The Indonesian Strong and Balanced Healthy Exercise (SI Kumbang) gymnastic exercise is a newly designed exercise model developed by researchers, which is a type of low-impact aerobic exercise with moderate intensity. SI Kumbang exercises are performed three times a week for 30 minutes over a period of 12 weeks. The main basis of these exercises is foot movements that follow a rhythm, with the feet rotating in sequence in the four cardinal directions.

**Objective:** This study aimed to evaluate and compare the impact of SI Kumbang gymnastic exercises and Bugar Lansia gymnastic exercise programs on physical performance and immunity in elderly.

**Methods:** A randomized single-blind clinical trial involved 66 elderly participants aged 60–70 years, divided into SI Kumbang (n=33) and Bugar Lansia (n=33) groups. Each group exercised three times weekly for 12 weeks. Outcomes measured for physical performance were cardiorespiration endurance using Six-Minute Walk Distance (6MWD), strength muscle using handgrip JAMAR, balance using Short Physical Performance Battery (SPPB), physical activity using Physical Activity Scale for the Elderly (PASE). Outcomes measured for immunity were inflamasome using Caspase-1 and IL-18. Data were analyzed using SPSS 29.0 tests with significance set at  $p<0.05$ .

**Results:** Physical performance in elderly showed, SI Kumbang group had significantly impact in cardiorespiration endurance (6MWD) ( $p=0.005$ ) and physical activity (PASE) ( $p=0.001$ ). However, there was no significant impact on strength muscle (handgrip JAMAR), and balance (SPBB). Immunity in elderly

showed, both group there were no significant in inflamasome Caspase-1 ( $p=0,055$ ) and IL-18 ( $p=0,255$ ).

**Conclusion:** In conclusion, SI Kumbang gymnastic exercise group has more significant impact in terms of physical performance, particularly in enhancing cardiorespiration endurance and physical activity rather than Bugar Lansia gymnastic exercise group. And there is no difference in physical performance aspects such as muscle strength, balance, and immunity aspects as Caspase-1 and IL-18 in the elderly.

**Keywords:** elderly, physical performance, immunity, SI Kumbang exercise gymnastics.

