## METHODS

This study was designed as a randomized clinical trial with allocation concealment and single blinding to assess how the "SI Kumbang" gymnastic exercise and the "Bugar Lansia" gymnastic exercise model affected physical performance and immunity in elderly. In cooperation with the Rehabilitation Medicine Polyclinics, the 12-week intervention took place at the Ahmad Dahlan Indoor Hall of RS Islam Jakarta Pondok Kopi, East Jakarta, between April until September 2025. According to the FI-40 score, the target demographic was made up of senior citizens who were categorized as robust and pre-frail. Patients who visited the Rehabilitation Medicine Polyclinics at RS Islam Jakarta Pondok Kopi during the study period were included in the accessible population.

Female participants between the ages of 60 and 70 who met the following inclusion criteria were categorized as pre-frail (FI-40 score  $> 0.08 < 0.25$ ) or robust (FI-40 score  $\leq 0.08$ ) and had a body mass index (BMI) between 18.5 and 24.9. Participants had to have managed diabetes mellitus (GDS  $\leq 120$  mg/dL) and blood pressure ( $\leq 130/80$  mmHg) without taking any drugs that affected heart rate. Only those who were willing to participate, able to adhere to the study procedures, and had not been enrolled in any organized exercise program in the previous three months were included. Chronic heart or lung conditions, chronic conditions that cannot be reversed (e.g., cancer or chronic renal disease), diabetes complications in the extremities, motor impairment (MMT  $< 5$ ), knee pain, lower limb deformities

(genu varus/valgus), and hand deformities were among the exclusion criteria. Dropouts were defined as those who did not finish the study, missed more than six workouts, or had negative outcomes linked to the intervention.

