A sample size of 33 people per group was determined. The study supervisor oversaw the use of a basic randomization program to carry out the random allocation. The Sequentially Numbered, Opaque, Sealed Envelope (SNOSE) technique was used to guarantee allocation concealment. Outcome assessors were subjected to single blinding; they were not told about group allocations and were not allowed to look for relevant information. The "SI Kumbang" and "Bugar Lansia" gymnastics exercise regimens were part of the intervention groups. For 12 weeks in a row, both therapies included three 30-minute sessions per week. Participants received adaption sessions to acquaint themselves with the workout regimens throughout the first week. The Borg Scale was utilized to track intensity.

The Six-Minute Walk Distance (6MWD) for cardiorespiratory endurance, and handgrip strength muscle measured using a handgrip JAMAR. The Physical Activity using Physical Activity Scale for the Elderly (PASE) questionnaire, the balance using Short Physical Performance Battery (SPPB) were among the outcome measures and the immunity aspect using inflammasome marker Caspase-1 and IL-18. The research team reviewed patient logbooks at the beginning of each week to track adverse effects such weariness, shortness of breath, pain, or dizziness. At RS Islam Jakarta Pondok Kopi, every suspected adverse event was swiftly assessed, and any required medical attention was given. Every adverse event was reported to the ethics committee of the institution.

Data analysis was performed using SPSS 29.0 tests with significance set at  $p<0.05$ . Descriptive summaries of the sample characteristics were provided. Prior to analysis, the normality of the data was checked. Dependent t-tests were used to compare pre intervention and post intervention score in the SI Kumbang and Bugar Lansia groups for normally distributed outcomes (6MWD, handgrip, SPPB, PASE, Caspase-1, IL-18); the Wilcoxon test was used to assess non-normal data. Independent t test or Mann-Whitney U test is used for compared the effectiveness of the two interventions ( $\Delta$  score). A p-value of less than 0.05 was deemed significant.

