## DISCUSSION

This study is the first to test the new SI Kumbang gymnastics exercise. Randomization has been performed, and the baseline demographic and clinical characteristics of the two groups are not different, except for IL-18, which shows a difference and is adjusted using ANCOVA.

From the clinical baseline data, the clinical picture of 6MWD, balance, and physical activity is less than normal. This illustrates the condition of elderly people who are generally inactive or sedentary in Indonesian society, that these three physical performances have indeed declined in elderly people entering the age of 60-70 years. In general, they will experience a decline in physical condition and health, especially in healthy elderly people who are inactive in sports, sedentary, or with various chronic diseases.

Other studies analyzed the relationship between sedentary time and physical endurance in elderly. They compared 83 older adults aged 60-87 years. Physical activity (light, moderate, or vigorous) and sedentary time were assessed using ActiGraph® GT1M Accelerometers (Fort Walton Beach, FL, USA). The Senior

Fitness Test assesses five physical fitness components (aerobic endurance, muscular strength, agility/dynamic balance, flexibility, and BMI), and includes six tests: 6-min walk distance (meters); chair stand test (repetitions/30 s); arm curl test (repetitions/30 s); 2.44 m up and go test (seconds); chair sit and reach test (centimeters); and back scratch test (centimeters). Regarding physical endurance, when compared to the inactive group, the active group achieved higher average results on aerobic endurance (6 min walk distance), upper and lower limb strength (arm curl and chair stand test, respectively), agility/dynamic balance. Elderly people are more likely to experience frailty, which many of us mistakenly believe to be a natural aspect of aging. It might be challenging to diagnose frailty in daily life and to differentiate between frailty syndromes and the normalcy associated with age vulnerabilities.

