## CONCLUSION

Both SI Kumbang and Bugar Lansia gymnastic exercises improved physical performance in older adults, as shown by significant gains in cardiorespiration endurance and physical activity in elderly. And there is no difference in physical performance aspects such as muscle strength, balance, and immunity aspects as Caspase-1 and IL-18 in the elderly.

These study results indicate that although both exercise modalities are effective in enhancing physical performance in elderly, SI Kumbang appears to provide superior benefits, particularly in improving cardiorespiration endurance and physical activity in elderly.

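### Table 1 counts 36 women per arm (72) under n=33 headings, the trial is reported as 66, and nothing in the document reconciles the two

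*Combined protocol and SAP*

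**What the plan says.** The abstract says the trial "involved 66 elderly participants aged 60–70 years, divided into SI Kumbang (n=33) and Bugar Lansia (n=33) groups". Methods states "A sample size of 33 people per group was determined" and gives no calculation or dropout allowance. The Result section repeats the total: "A total of 66 elderly participants in the study, divided into the" two groups. Tables 1 to 3 are all headed n=33 per arm.

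In Table 1, the row for female sex nevertheless reads 36 (100,0) in both columns.

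Two later statements depend on who was counted. The Discussion says "Randomization has been performed, and the baseline demographic and clinical characteristics of the two groups are not different", apart from IL-18. The Conclusion reports "no difference in physical performance aspects such as muscle strength, balance, and immunity aspects as Caspase-1 and IL-18"; for Caspase-1 this rests on p=0,055 in Table 3.

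Methods also contains a dropout rule: "Dropouts were defined as those who did not finish the study, missed more than six workouts, or had negative outcomes linked to the intervention". It gives no number of dropouts and does not say whether they were removed from the analysis.

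**The concern.** Thirty-six of 33 is impossible, so at least one of the heading, the counts or the stated total is wrong. If the baseline table covers 72 women and the outcome tests cover about 66, the document describes two different sets under one n.

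Three things are at stake:

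- **Who was randomised and who was analysed.** If randomised women were left out, the arms compared are not the arms as randomised, and the direction of any bias is unknown.
- **The baseline comparison.** The demographic part of the balance claim comes from a table that counts six more women than the trial reports. The clinical part comes from Table 2, also headed n=33.
- **Results near the threshold.** Caspase-1 at p=0.055 could move to either side of 0.05, depending on who is included.

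**Working it through.** **Step 1. Table 1 counts (SI Kumbang / Bugar Lansia).**

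| Variable | SI Kumbang | Bugar Lansia |
|---|---|---|
| Female | 36 | 36 |
| BMI class | 31+5 = 36 | 31+5 = 36 |
| Living history | 8+25+2+1 = 36 | 5+30+1+0 = 36 |
| Education | 1+2+5+16+12 = 36 | 2+5+3+14+11 = 35 |

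The one block that gives 35 contains 14 (41,7). Since 15/36 = 41.7%, the count is probably a slip.

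**Step 2. Table 1 percentages.** Each of the 32 printed percentages was recomputed as count/36 and count/33. Denominator 36 fits 27 of them. Denominator 33 fits one, the cell 0 (0), which fits any denominator. For example, 31/36 = 86.1% as printed, while 31/33 = 93.9%. Five cells fit neither: 14 (41,7), 10 (37,8) twice, 8 (23,2) and 3 (5,6).

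**Step 3. Table 3 t-tests.** Inputs are the printed changes, mean (SD), SI Kumbang against Bugar Lansia:

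- Caspase-1: -38945.33 (27628.63) against -24957.94 (30423.15), printed p 0.055
- Handgrip: 1.14 (2.69) against 2.06 (2.27), printed p 0.136
- PASE: 5.39 (4.38) against 1.16 (5.26), printed p 0.001

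For equal arms of size n, t = (m1 - m2) / (sp × √(2/n)), with sp = √((s1² + s2²)/2) and 2n - 2 degrees of freedom. The test is taken as two-sided; the document does not say.

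Caspase-1 at 33/33: the difference is -13,987.39, sp = 29,059.5 and SE = 29,059.5 × √(2/33) = 7,154.0. So t = -1.955 on 64 df, p = 0.0549, 95% CI -28,279 to +304. This reproduces the printed value.

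Caspase-1 at 36/36: SE = 29,059.5 × √(2/36) = 6,849.4, t = -2.042 on 70 df, p = 0.0449. This does not reproduce it.

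| Outcome | Printed p | p at 33/33 | p at 36/36 |
|---|---|---|---|
| Caspase-1 | 0.055 | 0.0549 | 0.0449 |
| Handgrip (rounding range) | 0.136 | 0.138 (0.133–0.143) | 0.121 (0.117–0.126) |
| PASE | 0.001 | 0.0007 | 0.0004 |

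Pooled and Welch tests agree. PASE excludes 36/36 only if 0,001 is a rounded exact value and not shorthand for less than 0.001.

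**Step 4. Which totals fit, one outcome at a time.** With arms of 20 to 36 and rounding allowed:

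- Caspase-1 fits totals of 66–67, so 72 - 67 = 5 to 72 - 66 = 6 women short (6.9–8.3% of 72).
- Handgrip fits 65–69, so 3–7 short.
- PASE fits 58–70, so 2–14 short.

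The split by arm is not identified. Caspase-1 fits 33/33, but also 32/34, 34/32 and more uneven splits out to 30/36 (Welch), 36/30 (pooled) and 36/31 (Welch). 6MWD, SPPB and IL-18 changes are medians with Mann-Whitney tests, so their n cannot be recovered.

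**Step 5. How much it could matter.** These are illustrations only. Each arm is filled from 33 to 36, and the added women are given that arm's SD.

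| Added women change like | Caspase-1 p | PASE p |
|---|---|---|
| Their own arm | 0.042 | 0.0003 |
| No change | 0.075 | 0.0013 |
| The other arm | 0.092 | 0.0033 |

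Over all splits that fit Caspase-1, its p ranges over 0.042–0.044, 0.011–0.30 and 0.083–0.094 in the three scenarios. PASE never exceeds 0.0064, and handgrip stays non-significant (0.063–0.34).

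**The case against.** The strongest reply accepts the mismatch and disputes what follows from it.

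- **This is a reporting inconsistency; no exclusion has been shown.** That stands. No available text says dropouts were removed. The dropout rule is one possible cause, alongside ordinary loss, missing assays or a different dataset behind Table 1.
- **The printed figures may contain slips.** Table 1 has five percentages that fit neither denominator, and 0.045 is one digit from 0.055. A slip cannot be excluded. However, 0.055 appears in the abstract, the results text and Table 3, and it matches 33/33, so 66–67 is the likelier reading for Caspase-1.
- **33/33 is not secure for every outcome.** If individual readings are whole numbers, which the document does not state, the SI Kumbang handgrip change of 1,14 needs 35 or 36 women and the Bugar Lansia PASE change of 1,16 needs 31 or 32 (among n of 30 to 36). This is weak evidence, but it points to n differing by outcome and so strengthens the request for n per outcome.
- **The fill-in p-values are scenarios, and the own-arm result falls below 0.05 by construction.** Agreed: they show sensitivity and predict nothing. It is also true that a p of 0.055 with that interval would not establish absence of a difference at any of these sample sizes; that is a separate matter.

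None of this offers a reading in which 72 and 66 agree. If Table 1 shows everyone randomised and Table 3 shows completers, the Table 1 heading and the stated total of 66 are wrong and the losses are unreported.

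**Conclusion.** The concern holds and must be fixed. Table 1 was built on 36 women per arm, 72 in all, and the trial is reported as 66. The Caspase-1 and handgrip tests do not come from 36 per arm if their printed means, SDs and p-values are right.

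The shortfall of 5 or 6 women applies to Caspase-1 alone; it extends to handgrip and PASE only if all three share one n. The split by arm, the cause and the direction of any bias are not established.

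Of the three outcomes that can be checked, only the Caspase-1 conclusion is sensitive to the gap. The PASE and handgrip conclusions do not change in the scenarios examined. 6MWD, the other positive result, cannot be checked.

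**What to change.** Reconcile first, from existing records:

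1. State the number randomised to each arm and explain 72 against 66.
2. Correct whichever headings, counts, denominators or totals are wrong in Tables 1 to 3, the results text and the abstract.
3. Report losses by arm with reasons, and the number analysed for each outcome, including 6MWD, SPPB and IL-18.

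Then act on what this shows:

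- **If 66 were randomised,** rebuild Table 1 on those 66. No re-analysis is needed on this ground.
- **If randomised women were left out,** make the main comparison all randomised participants in their assigned arm, using every available week-12 value and a stated missing-data method. Keep the 66-person analysis as a labelled sensitivity analysis.

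Reconciliation and corrected tables are cheap and need no new participants. Re-analysis, if needed, may give less favourable results. Where week-12 values do not exist, the results will depend on the missing-data assumption, which must be stated.

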## DISCUSSION

This study is the first to test the new SI Kumbang gymnastics exercise. Randomization has been performed, and the baseline demographic and clinical characteristics of the two groups are not different, except for IL-18, which shows a difference and is adjusted using ANCOVA.

From the clinical baseline data, the clinical picture of 6MWD, balance, and physical activity is less than normal. This illustrates the condition of elderly people who are generally inactive or sedentary in Indonesian society, that these three physical performances have indeed declined in elderly people entering the age of 60-70 years. In general, they will experience a decline in physical condition and health, especially in healthy elderly people who are inactive in sports, sedentary, or with various chronic diseases.

Other studies analyzed the relationship between sedentary time and physical endurance in elderly. They compared 83 older adults aged 60-87 years. Physical activity (light, moderate, or vigorous) and sedentary time were assessed using ActiGraph® GT1M Accelerometers (Fort Walton Beach, FL, USA). The Senior

Fitness Test assesses five physical fitness components (aerobic endurance, muscular strength, agility/dynamic balance, flexibility, and BMI), and includes six tests: 6-min walk distance (meters); chair stand test (repetitions/30 s); arm curl test (repetitions/30 s); 2.44 m up and go test (seconds); chair sit and reach test (centimeters); and back scratch test (centimeters). Regarding physical endurance, when compared to the inactive group, the active group achieved higher average results on aerobic endurance (6 min walk distance), upper and lower limb strength (arm curl and chair stand test, respectively), agility/dynamic balance. Elderly people are more likely to experience frailty, which many of us mistakenly believe to be a natural aspect of aging. It might be challenging to diagnose frailty in daily life and to differentiate between frailty syndromes and the normalcy associated with age vulnerabilities.

According to this study, elderly physical performance significantly improved because of both SI Kumbang and Bugar Lansia gymnastic exercise. Both groups showed substantial within-group improvements in the 6MWD, the same direction with a study by Casanova et al, which showed higher 6MWD values in the group that regularly performed aerobic exercise, with a 6MWD range of 380–782 meters. The impact of age on 6MWD became substantial at  $\geq 60$  years of age.

Significant variations in 6MWD can be explained by the gender, age, height, and weight of respondents. Degenerative diseases also increase with age, and even “apparently healthy” elderly people who are eager to participate in physical training sessions exhibit a wide range of health statuses.

Furthermore, a meta-analysis by Azimkhani et al. shows that endurance, aerobic, and combination exercise programs significantly improve cardiorespiratory endurance in older adults; the level of improvement depends on the intensity, duration, and adherence to the exercise program. Given the advanced age of the participants and the relatively short duration of the study intervention, these significant differences may be attributed to adequate exposure to training for improving cardiorespiratory endurance over 12 weeks, resulting in detectable physiological changes. Harber et al. emphasize that while improvement often requires sustained commitment to exercise therapy, accurate assessment of cardiorespiratory endurance, such as continuously increasing distance covered,

provides important insights into overall health and mortality risk.

This study shows that there is no significant difference between the muscle strength of the SI Kumbang exercise group and the Bugar Lansia exercise group as measured by handgrip strength. Handgrip strength is a valid and simple measure of our total body muscle strength. Grgic et al. support this by finding that an aerobic exercise regimen can increase muscle strength depending on the intensity of the exercise, duration, and type of exercise movements and exercise load required for significant hypertrophy and muscle strength changes. In the SI Kumbang exercise, a 0.5 kg barbell weight was given to the hands, which did not significantly affect muscle strength improvement compared to the Bugar Lansia exercise, which did not use barbell weights in the hands. Therefore, further studies are needed on the weight of the barbell and the type of movements that involve the core muscles or large muscles more to optimize muscle strength improvement.

The results of the balance difference analysis with SPPB scores show that there is no significant difference between the two exercise groups. SPPB is valid, reliable, responsive, and measures physical function in the elderly population. A change of 0.5 points on the SPPB is considered small but significant, while a change of 1 point is considered substantial. Lu et al. highlight the significance of aerobic exercise in maintaining or improving physical function by emphasizing the predictive validity of the SPPB and physical performance measures in identifying older adults at higher risk of falling over time. Both exercise programs showed an improvement in balance after exercise, and the two programs showed similar results. Ansai et al. provided aerobic exercise to elderly individuals for 16 weeks and found no significant difference between exercise and balance and the risk of falling because the elderly require a combination of multi-component muscle movements.

Physical activity in this study was significant for the SI Kumbang exercise group. In the elderly population, PASE scores were closely related to their functional abilities and overall health status. Higher PASE scores are often associated with better mobility, increased muscle strength, and a reduced risk of chronic diseases. According to Ayvat et al., PASE is a sensitive tool for identifying physical inactivity in the elderly population and successfully distinguishes between

active and inactive elderly individuals. The significant difference in PASE scores between the SI Kumbang exercise group and the control group in this study likely reflects the interaction between environmental, social, and daily behavioral factors that influence increased physical activity among the elderly outside of exercise activities. The increase in the average PASE score in the SI Kumbang exercise group shows a promising trend that could lead to a significant increase in physical activity levels and better functional health outcomes.

The decrease in Caspase-1 levels in both groups indicates that the exercise intervention successfully reduced inflammatory activity in older adults associated with inflammasomes. These results are in line with a systematic review by Bautmans et al., which found that various types of exercise, especially those combining resistance and aerobic components, can reduce Caspase-1 and other proinflammatory cytokines such as IL-1 $\beta$ , IL-6, and IL-18, thereby altering the inflammatory profile of older adults. The downregulation of inflammasome signaling pathways is demonstrated by the reduction in Caspase-1, a crucial enzyme that activates cytokines from the IL-18 family. Although there were no differences in changes between the two exercise groups.

Following exercise intervention, IL-18 levels did not decrease because the analysis of the process pathway showed that caspase-1 activation requires various processes to produce a decrease in IL-18, that activated caspase-1 will cleave the same tetrapeptide site in pro-IL-18. The crystal structure of the caspase-1 and pro-IL-18 complex reveals a two-site (binary) substrate recognition mechanism, a catalytic pocket that binds the tetrapeptide, and a unique exosome that critically recognizes GSDMD10 and binds to a specific structure formed jointly by the propeptide sequence and the post-cleavage site in pro-IL-18. This binary recognition is also used by caspase-1 to process pro-IL-18; structural deviations around the exosite underlie its inability to target rationally designed pro-IL-18. The structure of pro-IL-18 displays an autoinhibitory interaction between the propeptide and the post-cleavage site region, preventing recognition by the IL-18R $\alpha$  receptor.

Caspase-1 cleavage induces substantial conformational changes in IL-18 to generate two critical receptor binding sites and establishes IL-18 as a lipopolysaccharide-activated caspase-1 target. This finding represents a paradigm

shift in the understanding of noncanonical inflammasome-mediated defense and the function of IL-18 in immunity and disease. Thus, many important roles in the process of IL-18 reduction, which targets IL-18, are likely caused by gaps caused by the involvement of cytokines and other proteins in the signaling pathways of various inflammatory diseases other than IL-18. In this study, there were patients undergoing treatment for diabetes mellitus who may have influenced the increase in IL-18 in the two exercise groups. Chronic muscle injury in diabetes mellitus and the elderly can also cause an increase in IL-18. Although it was stated that 9 weeks of exercise could reduce IL-18 levels, the 12-week exercise intervention in this study was not able to reduce IL-18 levels. Another factor that could explain the lack of significant differences was that subjects were not prohibited from traveling outside the city and were not isolated during the exercise intervention.

